11.1. Participant Completion

Completion of the study will be defined as reaching the Week 58 visit.

11.2. Participant Stopping Rules and Withdrawal Criteria

Participants may be prematurely terminated from the study for the following reasons:

1. The participant elects to withdraw consent from all future study activities, including follow-up.
2. The participant is “lost to follow-up” (i.e., no further follow-up is possible because attempts to reestablish contact with the participant have failed).
3. The participant dies.
4. The Investigator no longer believes participation is in the best interest of the participant.
5. Individual safety stopping rules:

The participant experiences an allergic reaction to any IP (CoFAR Grade 4; see Table in section 12.3.1).

Table in section 12.3.1 (page 49)

- i. **CoFAR Grading Scale for Systemic Allergic Reactions Modified Version 2.0** Any subject deemed to have severe allergic reactions and who receives aggressive therapy (e.g., IV fluid resuscitation, mechanical ventilation, repeated doses of epinephrine for a life-threatening reaction) at any time should be discontinued from further therapy
- ii. Other circumstances including, but not limited to, the following:

- Severe adverse event, other than anaphylaxis, related to investigational product
- Pregnancy

11.3. Participant Replacement

Participants who withdraw or are withdrawn after initiation of home dosing will not be replaced.

11.4. Follow-up after Early Study Withdrawal

Subjects who prematurely discontinue treatment with OIT may remain in the study until end of study visit at week 58 to monitor safety and efficacy parameters. These visits will include skin testing and/or a blood draw for mechanistic studies at the study time points.

If the subject refuses this follow-up, or begins and then elects to discontinue the follow-up, they will be asked to come in for a final study visit consisting of a physical assessment, skin test, blood draw, review of their Food Allergy Action Plan, and instructions to discontinue any OIT dosing and continue food allergen avoidance.

11.5. Study Stopping Rules

During the course of this study, if the investigator or the NIAID Medical Officer discovers conditions that indicate that the study should be discontinued, an appropriate procedure for stopping the study pending DSMB review will be instituted, including notification of the FDA and IRB. See section 12.8.2.2

12. Safety Monitoring and Reporting

12.1 Overview

This section defines the types of safety data that will be collected under this protocol and outlines the procedures for appropriately collecting, grading, recording, and reporting those data. Adverse events that are classified as serious according to the definition of health authorities must be reported promptly (per Section 12.5, *Reporting of Serious Adverse Events and Adverse Events*) to the sponsor, DAIT/NIAID. Appropriate notifications will also be made to site principal investigators, Institutional Review Boards (IRBs), [replace with "Institutional Ethics Committees (IECs)", if applicable] and health authorities.

Information in this section complies with *ICH Guideline E2A: Clinical Safety Data Management: Definitions and Standards for Expedited Reporting*, *ICH Guideline E-6: Guideline for Good Clinical Practice*, 21CFR Parts 312 and 320, and applies the standards set forth in the National Cancer Institute (NCI), Common Terminology Criteria for Adverse Events (CTCAE), Version 5.0: <http://ctep.cancer.gov/reporting/ctc.html>.

12.2 Definitions

12.2.1 Adverse Event (AE)

Any untoward or unfavorable medical occurrence associated with the subject's participation in the research, whether or not considered related to the subject's participation in the research (modified from the definition of adverse events in the 1996 International Conference on Harmonization E-6 Guidelines for Good Clinical Practice) (from OHRP "Guidance on Reviewing and Reporting Unanticipated Problems Involving Risks to Subjects or Others and Adverse Events (1/15/07)" <http://www.hhs.gov/ohrp/policy/advevntguid.html#Q2>)

For this study, a related adverse event will include any untoward or unfavorable medical occurrence associated with:

- **Study therapy regimen:**
Home OIT Dosing

- Food allergy episodes in response to home dosing that are objective Grade 1 or 2 by Appendix 3 will be recorded on the paper AE CRFs and graded by CoFAR criteria.
 - Food allergy episodes in response to home dosing that are Grade 3 by Appendix 3 or that are classified as SAEs defined in Section 12.2.3 below will be recorded on the AE/SAE CRF as appropriate and graded by CoFAR criteria.
- **Study mandated procedures:**

For the procedures below, clinical situations are listed that are considered to be outside the normal range of outcomes and will be recorded as Adverse Events. These situations do not limit an investigator from recording and reporting any other events, associated or not with these procedures as AEs.

Allergen Skin Testing

- Prolonged (>24 hours) itching at test site
- Swelling (> 10 cm) at site of test lasting more than 24 hours
- Nasal allergic symptoms within 30 minutes from the procedure
- Fainting /Vasovagal event within 30 minutes from the procedure

Phlebotomy

- Bruising at phlebotomy site >5 cm with onset within 24 hours of procedure
- Erythema at phlebotomy site >5 cm with onset within 24 hours of procedure
- Infection at phlebotomy site
- Fainting /Vasovagal event within 30 minutes from the procedure

Spirometry or Peak Flow

- Feeling breathless
- Fainting/Vasovagal event within 30 minutes from the procedure

Double-Blind Placebo Controlled Food Challenges

During DBPCFCs, reactions will be recorded. DBPCFC material is not considered study drug, and as such, reactions will be recorded and reported separately.

12.2.1.1 Suspected Adverse Reaction (SAR)

Any adverse event for which there is a reasonable possibility that the investigational drug [or investigational study therapy regimen] caused the adverse event. For the purposes of safety reporting, 'reasonable possibility' means there is evidence to suggest a causal relationship between the drug and the adverse event. A suspected adverse reaction implies a lesser degree of certainty about causality than adverse reaction, which means any adverse event caused by a drug (21 CFR 312.32(a)).

12.2.2 Unexpected Adverse Event

An adverse event or suspected adverse reaction is considered "unexpected" if it is not listed in the Investigator Brochure or protocol, or is not listed at the specificity, severity or rate of occurrence that has been observed.

The Principal Investigator will review all adverse events related to skin prick testing, spirometry, DBPCFC, or other study procedures to determine if they are unexpected.

12.2.3 Serious Adverse Event (SAE)

An adverse event or suspected adverse reaction is considered “serious” if, in the view of either the investigator or Sponsor DAIT/NIAID, it results in any of the following outcomes (21 CFR 312.32(a)):

1. Death.
2. A life-threatening event: An AE or SAR is considered “life-threatening” if, in the view of either the investigator or Sponsor DAIT/NIAID, its occurrence places the subject at immediate risk of death. It does not include an AE or SAR that, had it occurred in a more severe form, might have caused death.
3. Inpatient hospitalization or prolongation of existing hospitalization.
4. Persistent or significant incapacity or substantial disruption of the ability to conduct normal life functions.
5. Congenital anomaly or birth defect.
6. Important medical events that may not result in death, be life threatening, or require hospitalization may be considered serious when, based upon appropriate medical judgment, they may jeopardize the subject and may require medical or surgical intervention to prevent one of the outcomes listed above.

Elective hospitalizations or hospital admissions for the purpose of conduct of protocol mandated procedures are not to be reported as an SAE unless hospitalization is prolonged due to complications.

12.3 Grading and Attribution of Adverse Events

12.3.1 Grading Criteria

The study site will grade the severity of non-allergic adverse events experienced by the study subjects according to the criteria set forth in the National Cancer Institute’s Common Terminology Criteria for Adverse Events (CTCAE) version 5.0. This document (referred to herein as the NCI-CTCAE manual) provides a common language to describe levels of severity, to analyze and interpret data, and to articulate the clinical significance of all adverse events. The NCI-CTCAE has been reviewed by the Principal Investigator and has been deemed appropriate for the subject population to be studied in this protocol.

Adverse events will be graded on a scale from 1 to 5 according to the following standards in the NCI-CTCAE manual:

- Grade 1 = mild adverse event.
- Grade 2 = moderate adverse event.
- Grade 3 = severe and undesirable adverse event.
- Grade 4 = life-threatening or disabling adverse event.
- Grade 5 = death.

Events grade 1 or higher will be recorded on the appropriate AE paper case report form (CRF) for this study.

For grading an abnormal value or result of a clinical or laboratory evaluation (including, but not limited to, a radiograph, an ultrasound, an electrocardiogram etc.), a treatment-emergent adverse event is defined as an increase in grade from baseline or from the last post-baseline value that doesn’t meet grading criteria. Changes in grade from screening to baseline will also be recorded as adverse events but are not treatment-emergent. If a specific event or result from a given clinical or laboratory evaluation is not included in the NCI-CTCAE manual, then an abnormal result would be considered an adverse event if changes in therapy or monitoring are implemented as a consequence of the event/result.

Clinical criteria for diagnosing anaphylaxis will be as follows (Sampson, HA, et. Al, 2006⁷⁹):

Anaphylaxis is highly likely when any one of the following 3 criteria are fulfilled:

1. Acute onset of an illness (minutes to several hours) with involvement of the skin, mucosal tissue, or both (eg, generalized hives, pruritus or flushing, swollen lips-tongue-uvula)
AND AT LEAST ONE OF THE FOLLOWING:
 - a. Respiratory compromise (eg, dyspnea, wheeze-bronchospasm, stridor, reduced Peak expiratory flow (PEF), hypoxemia)
 - b. Reduced blood pressure (BP) or associated symptoms of end-organ dysfunction (eg, hypotonia [collapse], syncope, incontinence)
2. Two or more of the following that occur rapidly after exposure to a likely allergen for that patient (minutes to several hours):
 - a. Involvement of the skin-mucosal tissue (eg, generalized hives, itch-flush, swollen lips-tongue-uvula)
 - b. Respiratory compromise (eg, dyspnea, wheeze-bronchospasm, stridor, reduced PEF, hypoxemia)
 - c. Reduced BP or associated symptoms (eg, hypotonia [collapse], syncope, incontinence)
 - d. Persistent gastrointestinal symptoms (eg, crampy abdominal pain, vomiting)
3. Reduced BP after exposure to known allergen for that patient (minutes to several hours):
 - a. Infants and children: low systolic BP* (age specific) or greater than 30% decrease in systolic BP
 - b. Adults: systolic BP of less than 90 mm Hg or greater than 30% decrease from that person's baseline

*Low Systolic BP is defined as less than $(70 + [2 \times \text{age}])$ mm Hg

Anaphylaxis severity will be graded according to the following CoFAR specific grading system scale:

Anaphylaxis Staging System

Staging System of Severity of Anaphylaxis	
Stage	Defined By
1. Mild (skin & subcutaneous tissues, GI, &/or mild respiratory)	Flushing, urticaria, periorbital or facial angioedema; mild dyspnea, wheeze or upper respiratory symptoms; mild abdominal pain and/or emesis
2. Moderate (mild symptoms + features suggesting moderate respiratory, cardiovascular or GI symptoms)	Marked dysphagia, hoarseness and/or stridor; shortness of breath, wheezing & retractions; crampy abdominal pain, recurrent vomiting and/or diarrhea; and/or mild dizziness
3. Severe (hypoxia, hypotension*, or neurological compromise)	Cyanosis or $\text{SpO}_2 \leq 92\%$ at any stage, hypotension, confusion, collapse, loss of consciousness; or incontinence

* https://ctep.cancer.gov/protocoldevelopment/electronic_applications/docs/CTCAE_v5_Quick_Reference_5x7.pdf

Other allergic reactions will be graded according to the following CoFAR specific grading system:

Table 4 COFAR Grading Scale for Systemic Allergic Reactions

Grade 1	Grade 2	Grade 3	Grade 4	Grade 5
---------	---------	---------	---------	---------


Reaction involving one of the following organ systems in which the symptoms are mild:
 
Cutaneous Generalized pruritus, generalized urticaria, flushing, angioedema
 
Upper respiratory Rhinitis, cough unrelated to laryngeal edema or bronchospasm
 
Conjunctival Injection/redness, itching, tearing
 
GI Nausea, abdominal pain (no change in activity level), single episode of vomiting and/or single episode of diarrhea
	
Reaction involving two or more of the following organ systems in which the symptoms are mild:
 
Cutaneous Generalized pruritus, generalized urticaria, flushing, angioedema
 
Upper respiratory Rhinitis, cough unrelated to laryngeal edema or bronchospasm
 
Conjunctival Injection/redness, itching, tearing
 
GI Nausea, abdominal pain (no change in activity level), single episode of vomiting, and/or single episode of diarrhea
	
Reaction involving:
 
Lower respiratory Throat tightness without hoarseness, wheezing, chest tightness, dyspnea, cough that responds to short- acting bronchodilator treatment (including IM epinephrine)
 
AND/OR
 
GI Severe abdominal pain, more than two episodes of vomiting and/or diarrhea
	
Reaction involving ANY of the following with or without other symptoms listed in Grades 1 to 3:
 
Laryngeal edema
 
AND/OR
 
Severe lower respiratory (throat tightness with hoarseness, wheezing, chest tightness, dyspnea, cough) including:
 
a) Refractoriness² to short-acting bronchodilator treatment (including IM epinephrine)
 
AND/OR
 
b) Hypoxia (O₂ saturation ≤92%)
	
Death

---	--	--	--	--------------

	
OR
 
Reaction involving one of the following organ systems in which the symptoms are moderate:
 
Cutaneous Generalized pruritus, generalized urticarial, flushing, angioedema
 
Upper respiratory Rhinitis, cough unrelated to laryngeal edema or bronchospasm
 
Conjunctival Injection/redness, itching, tearing
 
GI Nausea, abdominal pain (with change in activity level), two episodes of vomiting and/or diarrhea
		
AND/OR
 
c) Respiratory compromise requiring mechanical support
 
AND/OR
 
Cardiovascular Reduced BP with associated symptoms of end-organ dysfunction (e.g., hypotonia [collapse], syncope) defined as:
 
 • Children: low systolic BP (age specific¹) or >30% decrease in systolic BP • Adults: systolic BP of less than 90 mmHg or >30% decrease from baseline 	
--	---	--	---	--

1. Low systolic BP for children is defined as: less than 70 mmHg from 1 month to 1 year of age, less than (70 mmHg + [2 x age]) from 1 to 10 years of age, and less than 90 mmHg from 11 to 17 years of age.

2- For instance, this would include continuous nebulizer or epinephrine iv infusion or more than 3 epinephrine intramuscular injections

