4.2. Inclusion Criteria

Individuals who meet all of the following criteria are eligible for enrollment as study participants:

1. Subject and/or parent guardian must be able to understand and provide informed consent
2. Age 7 through 55 years (inclusive)
3. Clinical history of allergy to cashew or shrimp-containing foods
4. Serum IgE to cashew or shrimp of ≥ 0.35 kUA/L [determined by UniCAP™ within the past 12 months] and/or a SPT to cashew, or shrimp ≥ 3 mm compared to control
5. Experience dose limiting symptoms at or before the 300 mg challenge dose of FA protein on Screening DBPCFC conducted in accordance with PRACTALL guidelines
6. Written informed consent from adult participants
7. Written informed consent parent/guardian for minor participants
8. Written assent from minor participants as appropriate (e.g., above the age of 7 years or the applicable age per local regulatory requirements)
9. All female subjects of child-bearing potential will be required to provide a blood or urine sample for pregnancy testing that must be negative one week before being allowed to participate in the study.
10. Use of effective birth control by female participants of child-bearing potential

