- Comparing the proportion of participants who reach SU vs desensitized but SU failures at week 64 DBPCFC.

Safety Endpoints

- The proportion of participants with only mild AEs during the course of the study.
- The proportion of participants with respiratory or abdominal severe AEs during the course of the study.
- The proportion of participants who successfully pass a DBPCFC with no or mild objective reactions to a cumulative 2043 mg of the FA allergen at the end of OIT (week 52).
- The proportion of participants who successfully pass a DBPCFC with no or mild objective reactions to a cumulative 2043 mg of the FA allergen after 6 weeks off OIT (week 58).

Measurement: A DBPCFC is considered a “pass” if the subject has no dose limiting symptoms (appendix 3) during the challenge (from administration of first dose through observation period lasting 2 hours after administration of the final dose).

- Frequency of anaphylaxis.
- Frequency of use of epinephrine as a rescue medication.
- Frequency of AEs leading to premature withdrawal.
- Frequency of AEs in each treatment regimen leading to discontinuation of extended interval dosing.

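### The low systolic BP footnote to anaphylaxis criterion 3a has no upper age, so at ages 11–17 its cut-off is 92–104 mmHg, against 90 mmHg in Table 4 and in the adult line

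*Combined protocol and SAP*

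**What the plan says.** Section 12.3.1 (Grading Criteria) opens the diagnostic list with "Anaphylaxis is highly likely when any one of the following 3 criteria are fulfilled". Criterion 3 concerns a fall in blood pressure after exposure to a known allergen, and has two lines:

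- **3a:** "Infants and children: low systolic BP* (age specific) or greater than 30% decrease in systolic BP". The asterisk leads to a footnote, "Low Systolic BP is defined as less than" (70 + [2 × age]) mmHg. Neither the line nor the footnote says at what age a participant stops being a child.
- **3b:** "Adults: systolic BP of less than 90 mm Hg or greater than 30% decrease from that person's baseline".

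Later in 12.3.1, Table 4 grades allergic reactions other than anaphylaxis. Its footnote 1 also defines low systolic BP for children, but by age band. The 70 + 2 × age formula applies "from 1 to 10 years of age, and less than 90 mmHg from 11 to 17 years of age".

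Section 4.2 admits "Age 7 through 55 years (inclusive"), so ages 11 to 17 are in the trial. Section 13.2.2 lists "Frequency of anaphylaxis" among the safety measures.

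**The concern.** One section gives two cut-offs for the same named quantity, and they disagree for adolescents. Inside criterion 3 itself, the paediatric cut-off keeps rising with age and then falls abruptly to the adult value. Read literally, a 17-year-old with a systolic BP of 103 mmHg after a dose meets 3a, while an 18-year-old at 90 mmHg does not meet the 90 mmHg limit in 3b. Nothing in the protocol explains why an older adolescent should have a higher threshold than an adult.

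Because one criterion is sufficient, blood pressure alone can make the diagnosis. At stake is the count of anaphylaxis in 13.2.2, which could be slightly too high. A classification as anaphylaxis also sends the event to the three-stage anaphylaxis table instead of Table 4.

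**Working it through.** **Inputs.** The 3a footnote formula, adult line 3b and Table 4 footnote 1 (all 12.3.1); the age range (4.2).

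**Step 1: cut-offs by age.** For 3a the cut-off is 70 + 2 × age at every age. For Table 4 it is 70 + 2 × age up to 10, and 90 from 11 to 17. For example, at 10: 70 + 20 = 90; at 11: 70 + 22 = 92; at 17: 70 + 34 = 104.

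| Age | 3a footnote (mmHg) | Table 4 footnote 1 (mmHg) | Gap | Whole-number readings low under 3a only |
|---|---|---|---|---|
| 7 | 84 | 84 | 0 | none |
| 8 | 86 | 86 | 0 | none |
| 9 | 88 | 88 | 0 | none |
| 10 | 90 | 90 | 0 | none |
| 11 | 92 | 90 | 2 | 90–91 |
| 12 | 94 | 90 | 4 | 90–93 |
| 13 | 96 | 90 | 6 | 90–95 |
| 14 | 98 | 90 | 8 | 90–97 |
| 15 | 100 | 90 | 10 | 90–99 |
| 16 | 102 | 90 | 12 | 90–101 |
| 17 | 104 | 90 | 14 | 90–103 |

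The formula reproduces Table 4 exactly at ages 7–10 and departs from it at every age from 11. The mean gap over 11–17 is (2 + 4 + 6 + 8 + 10 + 12 + 14)/7 = 56/7 = 8 mmHg. The step from 3a to 3b at age 18 is 104 − 90 = 14 mmHg.

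**Step 2: dependence on where children ends.** Criterion 3 does not say. If at 10, the gap is 0; if at 12, at most 4 mmHg; if at 17, at most 14 mmHg.

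**Step 3: how far the 30% rule already covers these readings.** Both lines also count a fall of more than 30%. A reading r is such a fall from a starting value B only if r < 0.70 × B. I take B as the pre-dose systolic BP. That is an assumption, because only line 3b mentions a baseline.

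- Bottom of the band, r = 90: B = 128 gives a fall of 38/128 = 29.7% (not enough), and B = 129 gives 39/129 = 30.2%. So for any starting value up to 128 mmHg the footnote alone decides the whole band.
- Top of the band, r = 91, 93, 95, 97, 99, 101, 103 at ages 11 to 17: the smallest whole-number B that makes the reading a fall of more than 30% is 131, 133, 136, 139, 142, 145, 148. For example, 103/0.70 = 147.1, hence 148.

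The 30% rule therefore makes the footnote irrelevant only for adolescents who start at fairly high pressures.

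**Step 4: what is and is not affected.** A classification changes only if the participant is 11–17, the reading lies in the band, the fall is not above 30%, and criteria 1 and 2 are not met in some other way. The individual stopping rule in 11.2, "The participant experiences an allergic reaction to any IP (CoFAR Grade 4; see Table in section 12.3.1"), points to Table 4, which already has the age bands. The documents give neither the number enrolled at 11–17 nor the rate of such readings, so an expected count cannot be computed.

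**The case against.** The best counter-argument has four parts.

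- **The error is conditional.** Criterion 3 never says that children runs to 17, so the text may show only an unstated age limit. The condition is real. However, criterion 3 has just two groups, so an 11–17-year-old must fall into one of them, and the only age definition of children in 12.3.1 runs to 17. Even on another reading, staff have no stated age for moving from 3a to 3b.
- **The tools have different purposes.** Criterion 3a diagnoses anaphylaxis. Table 4 grades other reactions, and its Grade 4 blood-pressure item also requires symptoms of end-organ dysfunction. This stands, and it weakens the comparison with Table 4. It does not touch the mismatch between 3a and 3b, which lies within one criterion.
- **A reader could complete the short footnote from Table 4, or use judgement.** Criterion 3 is headed as a reduction in blood pressure, so a reading equal to the participant's usual value need not count. Clinicians may well act this way. But 3a carries its own explicit definition and does not refer to Table 4.
- **No consequence is shown, and the error is on the cautious side.** This largely stands. The affected measure is not in the 3.5 list and has no planned test. It is the reason for rating the point minor, but not a reason to leave the footnote uncorrected.

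**Conclusion.** The concern holds and is minor. The missing age cap and the arithmetic are certain. That 3a covers everyone under 18 is inferred from Table 4 footnote 1, with moderate confidence. On that reading the cut-off is 2 to 14 mmHg above both 90 mmHg comparators at ages 11–17. The direction is over-detection, so the frequency of anaphylaxis may be slightly over-counted, by an amount the documents do not allow anyone to calculate. Confidence that many events would change is low. Reactions that meet criterion 1 or 2 without relying on a blood-pressure reading are unaffected, as are the primary CD28 analysis, dosing and the rules based on CoFAR Grade 4.

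**What to change.** Replace the 3a footnote with the Table 4 bands: low systolic BP for children is below 70 + 2 × age mmHg at ages 1 to 10, and below 90 mmHg at ages 11 to 17. The cut-offs then run 84, 86, 88 and 90 at ages 7 to 10 and stay at 90 into adulthood, and the footnote itself settles where children ends. The staging table (which cites CTCAE for hypotension), synopsis stopping rule 5a, section 12.8.2.2 and Appendix 2 need no change.

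The cost is one footnote and no new data collection. Any 11–17-year-old already classified as anaphylaxis on 3a alone should be re-checked. It is sensible to include those who met criterion 1 or 2 only through its reduced-BP item, since those lines give no cut-off of their own and staff may have used the footnote.
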